398 study, we intentionally overrecruited. Recruitment continued until the end of January 2024,
399 aligning with the anticipated completion of our data collection period. As a result, a total of 63
400 participants consented, 50 of whom were randomized and completed the study.

401 *4.2 Recruitment and Eligibility*

[figure not shown]
402 The current sample was recruited from a database of previous participants in our lab and
403 via mental health agencies in the Dallas-Fort Worth region. Study fliers were placed in outpatient
404 clinics, and interested individuals either contacted study personnel directly or asked to be
405 contacted by the study team. This recruitment approach has been consistently used by our
406 research team supervised by [name], and has been found to yield a substantial number
407 of participants, respect patient privacy, and minimize the possibility of coercion.

408 Eligible participants were between the ages of 18 and 64 inclusively, had a diagnosis of
409 schizophrenia or schizoaffective disorder, and demonstrated either current (in the past week) or
410 recent (in the past month) paranoia. Participants were not asked to change any part of their
411 current treatment regimen, and all medications were accepted. Participants were required to have
412 been clinically stable for a minimum of 6 weeks with no dose changes $>20\%$ for a minimum of
413 two weeks. Exclusion criteria included: 1) presence or history of a pervasive developmental
414 disorder or mental retardation as defined by $IQ < 70$, 2) presence or history of neurological or
415 medical disorders that contraindicate neural stimulation (e.g. presence or history of epilepsy,
416 seizures, etc.), 3) demonstrating sensory limitations, including uncorrectable visual or hearing
417 impairments that interfere with assessment, 4) history of electroconvulsive therapy, 5) lack of
418 proficiency in English, and 6) substance use disorder not in remission in the past 6 months.

419
420 **5. Procedure**

421 As shown in **Figure 1** below, this was a double-blind, within-subjects, crossover design
422 comparing the effects of active vs. sham tDCS. Participants completed 3 long visits (i.e., 1
423 enrollment visit, 2 stimulation visits). The 2 stimulation visits were at least a week apart (with an
424 average of 14.58 days between the stimulation visits in the current study) to make sure that the

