425 tDCS effects from the first visit dissipated, and the first simulation visit was expected to occur 7
426 days after the enrollment visit (average days = 13.59 days in the current study).

Day 1 —→ Day 2-8 —→ Day 9 —→ Day 10-16 —→ Day 17 —→ Day 18-24

427

[figure not shown]
428 **Figure 1. Flowchart of the study procedure**

429

430 **6. Stimulation Protocol**

431 *6.1 Stimulation Procedure*

432 After completing pre-stimulation assessments, participants started the first stimulation
433 procedure of the visit via neuroConn's programmable Direct Current stimulator. Electrodes were
434 affixed to the participant's head to target the stimulation area as determined for each individual
435 via the international 10-20 EEG placement system with Modified Combinatorial Nomenclature.
436 For stimulating the right VLPFC, the anode was placed over F6 (Montreal Neurological Institute
437 coordinates: 44, 32, -12 (Pinkham, Hopfinger, Ruparel, et al., 2008), and the contralateral
438 homolog area (F5) was targeted for the stimulation of the left VLPFC (see **Figure 2** for 10-20
439 EEG placement). Electrodes were placed identically for the control condition. Following the
440 neurostimulation procedure, participants were asked to remain seated in the chair and browse
441 through magazines quietly for 30 minutes to allow stimulation effects to stabilize (Samani et al.,
442 2019).

443

444 **Figure 2. 10-20 EEG placement**

[figure not shown]
445 6.2 Counterbalance and Randomization

446 The active stimulation and sham control conditions were counterbalanced, meaning that
447 each participant had the same possibility of experiencing either the active or sham condition at
448 the first visit, and the other condition at the second visit. In the current study, 26 participants
449 received the active stimulation at their Visit 1, while the remaining 24 received it at their Visit 2.
450 This counterbalance procedure was achieved via the “study mode” preprogrammed feature of the
451 NeuroConn machine, which randomly assigned participants to either the active stimulation or
452 sham group in a double-blinded way. Specifically, each participant received a 5-digit code,
453 which was paired with one active stimulation code and one sham control code to ensure that each
454 participant did not receive two stimulation or control conditions. After study completion, each
455 participant’s study code for that given visit was revealed and recorded. The project manager

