456 maintained the list containing the condition information corresponding to each visit during the
457 study in case the blind conditions needed to be revealed in real time (e.g., if participants reported
458 adverse effects during tDCS).

459 *6.3 Stimulation Parameters*

The total stimulation time of 40 minutes was divided into two twenty-minute sessions to allow repeated stimulation, which may increase efficacy (Cheng et al., 2020; Kim et al., 2019). The active stimulation included active current at 2mA, ramping up over 15 seconds, sustaining for 20 minutes, and finally ramping down for 15 seconds. The dimensions of each electrode were 5 × 7 centimeters in size (35 cm^2), which led to a current density of 0.5714 mA/cm². For the sham condition, electrodes were still attached for 20 minutes each session, but the actual stimulation time was limited to 45 seconds per session, with 15 seconds of gradual stimulation, leading up to 15 seconds of full stimulation, and finally 15 seconds of ramping down. This limited stimulation mimicked the ramp up phase of active stimulation, making it more difficult for participants to guess the condition. The machine also automatically performed impedance control checks throughout the neurostimulation to ensure that both the participant and the experimenter could not tell which condition was being administered. Following each session,

472 inquiries into the participants' perceptions of the suspected condition showed that their accuracy
473 in identifying the correct condition was below chance levels (47%), supporting the efficacy of
474 the blinding procedures.

475

476 **Figure 3. Computational simulation of tDCS-induced current density.** (A) shows the
477 montage location in the study (1 = right VLPFC, 2 = left VLPFC). (B) reveals the distribution of
478 the current density estimated based on the stimulation location and parameters.

479

480 6.4 Current Modeling

481 To better characterize the current distribution during the stimulation, current modelling
482 was conducted for the active condition. This computational simulation utilized a finite element
483 model derived from MRI, implemented through the Comets toolbox (Jung et al., 2013) in Matlab
484 (<http://www.COMETStool.com>). **Figure 3** illustrates a detailed three-dimensional (3D)
485 numerical analysis of the current density generated by tDCS based on the montage applied in this

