679 It is possible that participants may feel tired, fatigued or anxious during the research
680 procedure; however frequent breaks were built into the lab portion of the study to reduce this
681 possibility. Additionally, participants were informed that they may take a break or terminate their
682 participation at any time. The most common side effect of tDCS neurostimulation is skin redness
683 just beneath the electrode. This effect usually wears off within one hour. Other potential risks
684 associated with tDCS include:

- 685 1. Itching at the electrode location; typically lasting less than an hour;
- 686 2. A small percentage of participants may experience mild dizziness upon stimulation onset.
687 After stimulation, this only lasts a few seconds and has no effect on balance;
- 688 3. Occasionally, temporary skin damage may occur beneath the electrode. This results in a week-
689 long darkening of the skin. At the planned current, the size of these marks, should they occur, is
690 only a few millimeters, posing a low risk;
- 691 4. After neurostimulation and the waiting period, participants may feel drowsy, but this effect
692 dissipates within one hour.

693 Finally, whenever information is gathered, there is a potential risk of loss of
694 confidentiality. This cannot be guaranteed, but every effort has been done to protect the privacy
695 of participants' information. Participants were assigned a random number that was used to
696 identify their data, and the file linking the number to the participants' email addresses and
697 birthdates was stored separately from the data they provide. This file will be erased upon
698 completion of the study. All data is stored in locked filing cabinets in secure offices at UTD, as
699 well as on password-protected/encrypted computers at UTD, and only study personnel who have
700 received extensive training in methods to protect confidentiality have access to the data.

701 *11.2 Potential Benefits*

702 It is possible that neurostimulation may reduce paranoid ideation and/or improve social
703 functioning for participants after active stimulation. However, the effects of tDCS are often
704 temporary, and we do not anticipate that such a short-term stimulation will have a lasting effect.
705 If this study is effective, subsequent research can investigate the ideal frequency and duration of
706 neurostimulation to deliver direct, long-lasting benefits.

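### No systematic collection or analysis of adverse effects is described, so the trial as documented gives no active-versus-sham tolerability comparison and would not reliably capture the week-long skin effect it lists.

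*Combined protocol and SAP*

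**What the plan says.** - **Effects listed.** Section 11.1 (Potential Risks) names redness as the most common effect, then itching, dizziness at onset, skin damage and drowsiness. The skin entry reads "Occasionally, temporary skin damage may occur beneath the electrode. This results in a week" and goes on to specify darkening, in marks of a few millimetres.
- **The only mention of handling.** Section 6.2 says that the project manager held the condition list during the "study in case the blind conditions needed to be revealed in real time (e.g., if participants reported" adverse effects while tDCS was running).
- **What is asked after a session.** Section 6.3 reports that "inquiries into the participants' perceptions of the suspected condition showed that their accuracy" was below chance, at 47%. No other post-session inquiry of this kind is described.
- **Visits.** Section 5 has one enrollment visit and two stimulation visits, with none after the second. It states that "The 2 stimulation visits were at least a week apart", with a mean gap of 14.58 days.
- **Order.** Section 6.2: "In the current study, 26 participants" "received the active stimulation at their Visit 1, while the remaining 24 received it at their Visit 2".
- **Remote contact.** Section 8 gives seven days of EMA after each stimulation visit, three surveys a day. Staff contact follows three consecutive missed surveys.

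**The concern.** The trial exposes each participant to active and sham stimulation in random order. That is a good setting for a within-person comparison of tolerability, yet the plan contains none. Section 1 justifies tDCS partly by its few adverse effects and tolerable experience, and Section 11.2 looks ahead to large-scale delivery to patients. If effects are not asked about, a low count of reported effects cannot be read as a low rate, and counts cannot be compared between conditions. A skin effect that appears or persists after the participant leaves could go unrecorded, which is also a loss for the participant concerned.

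**Working it through.** **Step 1. Set the listed effects against the described data collection.**

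| Effect (11.1) | Stated duration | Asked about or examined? |
|---|---|---|
| Redness | usually up to an hour | not described |
| Itching | typically under an hour | not described |
| Dizziness | seconds | not described |
| Drowsiness | up to an hour, after the waiting period | not described |
| Skin damage with darkening | a week | not described |

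Places checked:

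- Pre-stimulation measures (7.2): PS, SSPS, STAI-S. PANSS is also given at both stimulation visits (7.1).
- Between sessions (7.3 and Appendix A): SFS, cognitive, social-cognitive, trauma, mobility, morality and aggression measures. Section 7.3 refers to Appendix A for all measures given between sessions.
- Post-stimulation measures (headed 6.7, after 7.3): SSPS, STAI-S, AIHQ, SST, PID-5-HS, Trustworthiness Task.
- EMA (Appendix B, which Section 8 calls the complete list): Q1 to Q15 cover paranoia, voices, interaction and affect. Q9, on feeling energized, is an affect item and not a question about drowsiness after stimulation.
- Section 9: efficacy hypotheses 1a to 2b only.

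Result: 0 of 5 effects covered. Anxiety, which 11.1 gives as a possible reaction to the research procedure, is measured by STAI-S, but it is not one of the five.

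**Step 2. Which effects could be seen within the visit?** Participants sit for 30 minutes after stimulation (6.1, 7.3) and assessments follow. Four of the five effects last at most about an hour, so they fall largely inside attended time. Only the skin effect clearly outlasts the visit.

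**Step 3. Which participants return after active stimulation?** 26 + 24 = 50, which reproduces the number of completers. 24/50 = 48% had active stimulation at their last visit. The other 26/50 = 52% had one later visit.

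**Step 4. Does that later visit catch a week-long mark?** The minimum gap is 7 days, and the Figure 1 schedule gives 17 − 9 = 8 days. The mean gap for the whole sample is 14.58 days, and 14.58 − 7 = 7.58 days beyond a week. A week-long mark could have gone before Visit 2, and no skin check is described at that visit.

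**Step 5. What would full collection give?** The documents state no event rate, so rates here are assumptions. If all 50 were asked after active stimulation, the chance of at least one case is 1 − (1 − p)^50:

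| Assumed rate p | Chance of at least one case in 50 |
|---|---|
| 1% | 39% |
| 2% | 64% |
| 5% | 92% |
| 10% | 99% |

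The trial is large enough to show common effects and too small to exclude rare ones.

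**The case against.** The case on the other side has four parts.

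- *The trial tests efficacy only.* Goals 1 and 2 and all hypotheses concern paranoia and social functioning, and the statement about few adverse effects is background. This stands to the extent that the efficacy analyses are untouched. It does not remove the value of a comparison that the design offers at almost no cost.
- *Silence is not proof.* The Figure 1 image is not shown, consent pages were removed, and a separate main article is cited. This stands as a limit on wording: the claim is that collection is not described, not that nobody looked. The measure lists are nevertheless present as text, and the documents present Appendices A and B as full accounts of their parts.
- *Staff are present and EMA follows.* Correct, but no EMA item asks about side effects and the described call is triggered by missed surveys.
- *Data collection is over.* Recruitment ran to the end of January 2024 and the document is dated November 2024. This stands, and it makes the reporting statement in the fix the decisive part for this trial.

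Some stronger readings are tempting and should not be drawn:

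- A reader might take Section 6.2 as a rule that effects are acted on only if volunteered during stimulation. It is one example of breaking the blind. It sets no such limit and does not say that reports must be unprompted.
- A reader might infer that most listed effects occur when nobody is present. Step 2 shows otherwise.
- A reader might treat the 26 as followed and the 24 as not, and compare zero-event upper bounds of 10.9% and 5.8%. No skin check is described for the 26 either, so that contrast has no basis.
- A reader might infer that a lingering mark unblinds the experimenter at Visit 2. That needs the mark to last long enough, to be noticed, and not to occur under sham. The documents support none of these.
- A reader might see a contradiction between a week-long mark and a minimum gap of a week. The two are compatible.

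**Conclusion.** The point holds in this limited form. None of the five listed effects is covered by a described question, examination or analysis, so the documents provide no tolerability comparison between active and sham. The gap matters most for the week-long skin effect: 48% of completers have no visit after active stimulation, and the return visit of the other 52% is too late, on average, to be a reliable check. This is a worthwhile and inexpensive improvement, not a flaw in the efficacy analysis.

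It rests on two assumptions: that the available text describes all assessments made, and that the 26/24 split of completers is the relevant base. Section 4 reports 62 enrolled with 12 not completing, and Section 4.1 reports 63 consented. Whether any non-completer was stimulated is not stated.

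**What to change.** 1. At each stimulation visit, after the last condition guess of that visit, ask a fixed checklist of the five effects in 11.1, covering both sessions, and record any visible electrode-site effect. Guesses are taken after each session, so a checklist after session 1 could influence the next guess. Placing it last avoids this within the visit.
2. In the seven days of EMA after each stimulation visit, add one item on any skin or other problem since stimulation.
3. Add to Section 9 a within-person active-versus-sham tabulation of these effects, with denominators. Section 8 reports 47 of 50 with full EMA data, so 50 − 47 = 3 would be missing from the EMA item.
4. If these data were not collected, state in the SAP and the report that the trial gives no tolerability comparison. If any adverse-effect records exist, tabulate them by condition and say how they were obtained.

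Any decision about re-stimulation stays with the investigator.

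Cost: about a minute per visit, one EMA item (on up to 3 × 7 = 21 surveys per period) and one table, using existing staff and contacts. Solicited counts will be higher than spontaneous ones. A checklist at Visit 1 still precedes the guesses at Visit 2, so it should be identical at both visits.

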APPENDIX A: SUPPLEMENTARY MEASURES

MATRICS Consensus Cognitive Battery (MCCB; Stimulation Visit 1). The MCCB (Nuechterlein et al., 2008) was used to capture cognitive function, including processing speed (Trail Making Test: Part A, Animal Naming), working memory (Letter-Number Span), and verbal learning (Hopkin's Verbal Learning Test-Revised). Previous research has found impaired cognitive profiles in patients with schizophrenia (Kern et al., 2011).

Wisconsin Card Sorting Test (WCST; Stimulation Visit 1). The WCST (Berry et al., 2015; Nelson, 1976) was used to assess executive function (e.g., planning, set changing capacity). In this task, 4 stimulus cards and 64 response cards were presented on the computer. Participants were asked to match each response card to one of the stimulus cards according to one of three possible criteria (i.e., color, shape, or number). Immediately following each sort, participants were informed if they were correct or incorrect. After 10 correct sorts, the sorting rule changed, and participants had to discover a new rule. A subsequent string of 10 correct responses triggered another rule change, and this continued until all 64 cards were sorted. The number of categories/criteria achieved, total errors, and perseverative errors (i.e., when the card is sorted according to a category concept that the participant was told was erroneous) were calculated. Previous research has found that more perseverative errors were made by schizophrenia patients with paranoid ideations compared to healthy controls (Berry et al., 2015).

The Fast and Slow Thinking Questionnaire (FaST; Stimulation Visit 1). The FaST (Hardy et al., 2020) contains 10 items measuring fast and slow thinking biases when having paranoid thoughts on a 5-point scale (1 = not at all, 5 = totally; range = 10-50), with higher scores indicating higher proneness for fast or slow thinking. This measure was included because previous research has suggested the involvement of fast and slow thinking biases in paranoia in both clinical and general populations (Garety et al., 2021; Hardy et al., 2020).

Childhood Trauma Questionnaire (CTQ; Stimulation Visit 1). Given that trauma has previously been associated with paranoia (Freeman et al., 2002; Freeman & Fowler, 2009), we used the CTQ Short Form (Bernstein et al., 2003) to assess childhood trauma and control for it. The CTQ Short Form contains 28 items (e.g., “People in my family said hurtful or insulting things to me”, “I believed that I was physically abused”) on a five-point scale (1 = never true, 5 = very often true). Scores range from 28-140, with higher scores indicating higher level of childhood trauma.

Penn Emotion Recognition Task (ER-40; Stimulation Visit 1 and 2). The ER-40 was used to assess emotion recognition ability (Kohler et al., 2003). Forty color photographs of faces expressing one of 4 basic emotions (happiness, sadness, anger, fear) or a neutral expression were presented to the participants. After viewing each face, they were asked to choose the correct emotion. The dependent variable consists of the accuracy score ranging from 0 to 40, with a higher score indicating higher emotion recognition ability. Impaired ER-40 performance was observed in patients with schizophrenia (Butler et al., 2009), but inconclusive results were reported in studies on individuals with prominent paranoid ideation. Previous research found nonsignificant differences in ER-40 performance between paranoid and non-paranoid patients with schizophrenia (Pinkham, Harvey, et al., 2016); however, individuals with subclinical paranoia showed reduced accuracy in identifying negative emotions compared to individuals with low paranoia (Combs et al., 2013). Some studies also reported that paranoid patients are more likely to misinterpret neutral facial expressions as angry and threatening (Pinkham et al.,

757 2011; Tso et al., 2015).

758 ***Bell Lysaker Emotion Recognition Test (BLERT; Stimulation Visit 1 and 2).*** The
759 BLERT (Bell et al., 1997) measures the ability to recognize seven emotions: happiness, sadness,
760 fear, disgust, surprise, anger, or no emotion. Twenty-one videos (each one lasts ~10 seconds) of
761 a single male actor were presented, which include facial, verbal, paraverbal, and body movement
762 information. Participants were asked to view these segments and identify the emotion shown.
763 The total number of correct identifications was used to reflect performance (range = 0-21), with a
764 higher score indicating better emotion recognition ability. The BLERT has good psychometric
765 properties in both clinical and general populations (Pinkham, Penn, et al., 2016), and has
766 demonstrated high sensitivity and specificity in differentiating individuals with varying degrees
767 of social cognitive deficits (Hajdúk et al., 2018).

768 ***Hinting task (Stimulation Visit 1 and 2).*** The Hinting task was used to assess the ability
769 to infer the true intent of interpersonal conversations (Corcoran et al., 1995). Ten short passages
770 were read aloud, each of which is a social interaction between two characters and ends with one
771 of the characters providing a hint. Participants were asked to indicate what they think the
772 character truly meant. Responses are scored in real-time, and if a correct response is not given
773 after the first hint, a second hint is provided. Each item is thus scored as either 0 = incorrect
774 response, 1 = correct response after second hint, or 2 = correct response after first hint. Difficulty
775 in mentalizing/Theory of Mind (ToM) as measured by the Hinting task has been linked to more
776 auditory hallucinations in patients with psychosis and more paranoid-like experiences in non-
777 psychotic first-degree relatives (Versmissen et al., 2008). Performance on the hinting task also
778 moderated the relationship between paranoia and social functioning, as revealed by a study of 88
779 adult patients with SSD, which found a negative correlation between paranoia and social
780 functioning in patients with hinting scores in the bottom 78th percentile, but such a correlation
781 became nonsignificant for patients with hinting scores in the top 22nd percentile (Phalen et al.,
782 2017).

783 ***Residential mobility history (Stimulation Visit 1).*** Residential mobility is the frequency
784 that an individual moves from one place to another (Oishi, 2010). Residential mobility has been
785 found to be associated with a greater desire to expand one's social network (Oishi et al., 2013),
786 but also with poorer emotional and behavioral outcomes (Jolleyman & Spencer, 2008) and lower
787 well-being (Oishi & Schimmack, 2010). Therefore, to investigate the relationship between
788 residential mobility and paranoia, we collected data on the history of residential mobility in this
789 study. Participants were asked to indicate the number of times that they have moved from one
790 city/town to another since birth, followed by a list of all cities/towns to which they have moved
791 and their ages when they moved (Oishi, 2010).

792 ***Social norm violation task (SNVT; Stimulation Visit 2).*** Recent studies investigating
793 how paranoia affects social decision-making found that paranoia was associated with decreased
794 cooperation and increased punishment towards partners in economic games (Raihani et al., 2021;
795 Raihani & Bell, 2018). In this study, we measured social norm violation perception to test its role
796 in paranoia and aggression. In this social norm violation task (Mu et al., 2015), participants rated
797 the appropriateness of 48 norm-violating behaviors (e.g., "John is talking on his cell phone in the
798 movie theater") on a 7-point scale (1 = strongly inappropriate, 7 = strongly appropriate). All
799 items were reverse-coded, and higher scores reflect being more critical towards the violation.

800 ***The Moralism Scale (MS; Stimulation Visit 2).*** The MS (Janoff-Bulman et al., 2009)

801 was used to further measure the perception of prescriptive (i.e., did not do the good thing, for
802 example, did not help others) and proscriptive (i.e., do the bad thing, for example, cheat or steal)
803 moral violation in the current study. The MS contains 20 scenarios where the character is
804 considering conducting a certain moral (violation) behavior or not (10 items for prescriptive
805 morality and 10 for proscriptive morality). Participants indicated whether the character in each
806 situation should or should not do the behavior on a 9-point scale (1 = feel very strongly he/she
807 should not do, 9 = feel very strongly he/she should). Scores were calculated for prescriptive and
808 proscriptive (will be reverse-coded) morality, respectively, with higher scores indicating a higher
809 weight has been assigned to prescriptive or proscriptive morality.

810 ***Aggression Questionnaire (AQ; Stimulation Visit 2).*** The AQ includes 29 items
811 assessing aggressive behavior and tendencies across 4 dimensions: physical aggression, verbal
812 aggression, anger, and hostility (Buss & Perry, 1992). It is rated on a 5-point scale ranging from
813 1 (extremely uncharacteristic of me) to 5 (extremely characteristic of me), with higher scores
814 indicating higher levels of aggression. In previous research, a significant positive correlation was
815 found between persecutory ideation and aggression reported via AQ in both individuals with
816 SSD and the general community (van Dongen et al., 2011).

817 ***Novaco Anger Scale and Provocation Inventory (NAS-PI; Stimulation Visit 2).*** The
818 NAS-PI is another self-reported measure examining anger reactions in everyday life (Novaco,
819 2003). The first part of NAS-PI contains 48 items tapping in to 3 dimensions: cognitive, arousal,
820 and behavioral. Participants rated each item along a 3-point scale (1 = never true, 3 = always
821 true), with higher scores indicating higher levels of aggression tendency. The second part
822 contains 25 items depicting provoking situations, and participants rated how angry each of them
823 makes them feel on a 4-point scale (1 = not at all angry, 4 = very angry), with higher scores
824 indicating higher anger disposition. Good psychometric properties have been demonstrated
825 among individuals with psychotic disorders (Novaco, 2003), and previous research has found
826 that NAS-PI was positively associated with the suspiciousness item of PANSS in individuals
827 with psychotic disorders (Bucci et al., 2013)

